- patient has at least 1 daytime urinary urgency incontinence episode over the 2-day diary collection period
- PVR urine volume must be < 200 mL
- at least 12 weeks have elapsed since the patient’s previous study treatment
- patient has not experienced a serious treatment-related adverse event at any time

Treatment will be administered within 4 weeks (28 days) after a patient qualifies for retreatment.

Retreatment(s) can be administered up to 96 weeks from randomization on day 1 and will only occur once all “day of treatment criteria” are fulfilled (see Section 5.9.1).

Treatment will be administered via cystoscopy (rigid or flexible cystoscope) as 20 intradetrusor injections of 0.5 mL each evenly distributed, sparing the trigone. Administration can be under local anesthesia (with or without sedation), or general anesthesia.

Randomization/Stratification: Patients will initially be randomized on day 1 to one of 3 treatment groups in a 1:1:1 ratio:

- 25 U BOTOX (not to exceed 6 U/kg)
- 50 U BOTOX (not to exceed 6 U/kg)
- 100 U BOTOX (not to exceed 6 U/kg)

Patients will be centrally randomized and assigned a randomization number prior to treatment. In order to ensure balance across treatment groups, patients will be stratified by baseline daytime urinary urgency incontinence episodes (a total of ≤ 6 episodes or > 6 episodes over the 2-day diary collection period).

Doses received at subsequent retreatments will be determined by the investigator and will be based upon the patient’s response to their previous treatment.

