- patient currently uses or plans to use medications or therapies to treat symptoms of OAB, including nocturnal enuresis or nocturia. Patients previously receiving these medications must have discontinued their use prior to the start of the first screening procedures as follows:
 - for desmopressin, at least one day prior
 - for anticholinergic therapy, at least 7 days prior
 - for intravesical anticholinergic therapy, at least 4 weeks prior
 - for mirabegron, at least 14 days prior
 - patient currently uses or plans to use an implantable or nonimplantable electrostimulation/neuromodulation device for treatment of OAB. (If a nonimplantable device is used, it must be discontinued at least 7 days prior to the first screening procedure; if a device is implanted, it must be inactive for at least 4 weeks prior to the first screening procedure; neither should be used during the study.)
 - patient uses CIC or an indwelling catheter to manage their OAB
 - patient has had previous or current botulinum toxin therapy of any serotype for any urological condition, or treatment with botulinum toxin of any serotype within 3 months of randomization/day 1 for any other condition or use
 - patient has been treated with intravesical capsaicin or resiniferatoxin within 12 months of screening
 - patient has a post-void residual (PVR) urine volume of > 40 mL at screening. The PVR measurement can be repeated once on the same day; the patient is to be excluded if the repeated measure is above 40 mL.
 - patient has a daytime (waking hours) total volume of urine voided > 3000 mL, collected over one daytime period during the 2-day bladder diary collection period prior to randomization/day 1
 - postmenarche female patients of childbearing potential who are pregnant, nursing, or planning to become pregnant during the study (postmenarche female patients must also either be sexually abstinent or use another acceptable form of contraception – see Section 4.5.1.1)
 - patient has known allergy or sensitivity to components of any botulinum toxin preparation (including the study medication preparation), anesthetics or antibiotics to be used during the study
 - patient has hemophilia, or other clotting factor deficiencies, or disorders that cause bleeding diathesis

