 9. patient plans to start using psychiatric medications or medications for attention deficit hyperactivity disorder during the study. If the patient is already using such medications they should be on a stable dose prior to randomization/day 1 and agree to remain on the same dose during the study if possible when medically indicated.
 10. patient uses CIC or an indwelling catheter to manage their OAB
 11. patient has had previous or current botulinum toxin therapy of any serotype for any urological condition, or treatment with botulinum toxin of any serotype within 3 months of randomization/day 1 for any other condition or use

12. patient has been treated with intravesical capsaicin or resiniferatoxin within 12 months of screening
13. patient has a PVR urine volume of > 40 mL at screening. The PVR measurement can be repeated once on the same day; the patient is to be excluded if the repeated measure is above 40 mL.
14. patient has a daytime (waking hours) total volume of urine voided > 3000 mL, collected over one daytime period during the 2-day bladder diary collection period prior to randomization/day 1
15. postmenarche female patients of childbearing potential who are pregnant, nursing, or planning to become pregnant during the study (postmenarche female patients must also either be sexually abstinent or use another acceptable form of contraception – see Section 4.5.1.1)
16. patient has known allergy or sensitivity to components of any botulinum toxin preparation (including the study medication preparation), anesthetics or antibiotics to be used during the study
17. patient has hemophilia, or other clotting factor deficiencies, or disorders that cause bleeding diathesis
18. patient cannot withhold any antiplatelet, anticoagulant therapy, or other medications with anticoagulant effects for 3 days prior to randomization/day 1. Note: some medications may need to be withheld for > 3 days, per clinical judgment of the investigator (see Section 4.5.2, Prohibited Medications/Treatments for additional details)
19. patient has any medical condition that may put them at increased risk with exposure to BOTOX including diagnosed myasthenia gravis, Eaton-Lambert syndrome, or amyotrophic lateral sclerosis
20. current enrollment in an investigational drug or device study, or participation in such a study within 30 days of entry into this study (or longer if local requirements specify)

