#### **5.1 Collection of Primary Efficacy Measurement(s) and Derivation of Primary Efficacy Variable(s)**

The following efficacy measures will be collected and summarized by BOTOX treatment cycle, BOTOX dose group, and all BOTOX group on the BOTOX-treated population:

- number of daytime urinary incontinence episodes
- number of daytime micturition episodes
- number of daytime urgency episodes
- presence or absence of nighttime urinary incontinence
- volume voided per micturition
- time to patient's request and time to patient's qualification for retreatment
- pediatric incontinence questionnaire (PinQ) score
- modified treatment benefit scale (TBS)

Change from study baseline analyses will be performed. Study baseline is defined as the data collected prior to the first treatment.

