### **6.6.3 Post-void Residual (PVR) Urine Volume**

Summary statistics for mean values at each visit, baseline and mean change from study baseline, and 95% CI for the mean change from baseline at each applicable visit will be tabulated by treatment group.

As per the protocol guidance, patients with elevated PVR or patients who initiated clean intermittent catheterization (CIC) may have further specific follow-up visits where PVR and the need for CIC are evaluated. Therefore, these patients may have multiple post-baseline PVR values recorded within 1 visit window, and in those cases, the highest PVR value will be presented in the summary table.

The proportion of patients with total PVR urine volume of  $\leq 100$ ,  $> 100$  to  $< 200$ ,  $\geq 200$  to  $< 350$  and  $\geq 350$  mL will be summarized by treatment group and visit for each BOTOX treatment cycle.

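### In cycles 2 onward the PVR tables have no comparison with the pre-retreatment value, so residual urine left from an earlier injection can be attributed to the new cycle and its dose

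*Protocol*

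**What the plan says.** **Entry.** Protocol 4.4 excludes a patient if "patient has a PVR urine volume of > 40 mL at screening"; one same-day repeat is allowed.

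**Retreatment.** The Protocol Summary and section 5.10.1 require only "PVR urine volume must be < 200 mL". The reading is taken at the qualification visit, and the day-of-treatment criteria in 5.9.1 refer back to it. Table 1 marks no PVR at the retreatment visit itself.

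**Continuous summary.** SAP 6.6.3 plans "Summary statistics for mean values at each visit, baseline and mean change from study baseline, and 95% CI for the mean change from baseline" for each applicable visit and treatment group.

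**Reference value.** SAP 5.1 states: "Study baseline is defined as the data collected prior to the first treatment". That sentence sits in the efficacy section, but 6.6.3 uses the same term, and SAP 6.4 and 6.6.7 define it in the same way for laboratory values and eGFR.

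**Bands.** SAP 6.6.3 adds "The proportion of patients with total PVR urine volume of" ≤100, >100 to <200, ≥200 to <350 and ≥350 mL, which "will be summarized by treatment group and visit for each BOTOX treatment cycle".

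**Dose label.** Under SAP section 6, safety results in each cycle are grouped by the dose actually given in that cycle.

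No section of either document uses the qualification-visit PVR as a reference for the cycle that follows it.

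**The concern.** PVR is a central safety measure for this treatment. Protocol section 1 reports that it was dose-dependent in the adult phase 2 study, and safety of repeated treatment is a stated objective. In cycle 1 the study baseline is also the value before the injection, so change from baseline describes that injection. From cycle 2 on, the study baseline is still at most 40 mL, but a patient may receive the next injection with any volume below 200 mL. The planned tables then combine what was present before the injection with what followed it, and show the total under the new cycle and its dose. A reader assessing repeat treatment could not tell a new PVR elevation from one that was already there.

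**Working it through.** The documents give no computed figure for this point, so there is none to reproduce. The check is bounding arithmetic on two thresholds and a reporting rule.

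**Inputs**
- b, study-baseline PVR: 0 to 40 mL (Protocol 4.4).
- q, PVR at qualification: 0 to 199 mL in whole mL (Protocol 5.10.1).
- f, PVR at a visit in the new cycle.

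**Decomposition.** Change from study baseline = f − b = (f − q) + (q − b). The first term is the change since the last reading before the injection. The second was there beforehand.

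**Bound for one patient.** Suppose the earlier residual persists and the new injection adds nothing, so f = q and f − q = 0. The table then shows q − b:
- q = 199: 199 − 0 = 199 mL, or 199 − 40 = 159 mL.
- q = 150: 150, 130 and 110 mL for b = 0, 20 and 40.
- q = 100: 100, 80 and 60 mL for b = 0, 20 and 40.

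**Shift in a group mean.** If a share s of retreated patients carries an excess e = q − b, the mean change is raised by s × e. The documents give neither quantity; these values are assumptions, with e running from 60 to 199 mL:
- s = 5%: 0.05 × 60 = 3.0 mL to 0.05 × 199 ≈ 10.0 mL.
- s = 10%: 6.0 to 19.9 mL.
- s = 20%: 12.0 to 39.8 mL.

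**Bands.** With f = q, a value of 101 to 199 mL falls in the >100 to <200 mL band of the new cycle. Carry-over alone cannot enter the ≥200 mL bands, because retreatment requires less than 200 mL. It does alter the rise needed to get there: 200 − 199 = 1 mL from the highest qualifying value, against 200 − 40 = 160 mL from the highest study baseline.

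**Can the pre-injection value be recovered from the planned tables?** Not reliably. SAP 2.2 counts days from the most recent treatment, so the qualification visit belongs to the previous cycle. If week 12 is attended on day 85 and qualification on day 100, both lie in the Day 65 to Day 127 window, and one value represents it: the one nearest the target day or, for patients with elevated-PVR or catheterization follow-up, the highest (SAP 6.6.3). Even when the qualification reading is the one shown, it is not paired with the readings that follow.

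**Comparison with adverse events.** SAP 6.2 counts an event that began before a cycle's treatment in that cycle only if it then worsened or became serious. PVR has no matching rule.

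**The case against.** The case on the other side is substantial, and most of it limits the size of the point.

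- **Other outputs exist.** A reader might infer that PVR in later cycles is reported solely as change from study baseline. It is not: visit means and absolute bands are also planned. They do not cure the problem, because absolute values contain the same carried-over volume.
- **Carry-over is possible, not shown.** It requires PVR to remain raised at least 12 weeks after an injection, in a patient whose urgency incontinence is present again, and then to persist into the new cycle. Protocol section 1 describes the adult rise at 100 U as transient and, in most patients, no more than 100 mL. This stands.
- **Events and higher bands are largely protected.** A reader might infer that retention counts are inflated too. The SAP 6.2 cycle rule prevents that for adverse events of retention and residual urine, and carry-over alone cannot reach the bands that trigger protocol action. The exposed band, >100 to <200 mL, requires none under Protocol 6.3.9. This stands.
- **Attribution to a higher dose is less likely than attribution to a later cycle.** Protocol 5.5 allows an increase only if the preceding dose was well tolerated. This stands.
- **Study baseline is a legitimate reference.** It is used throughout the SAP and shows total departure from the untreated state. The randomised comparison is in cycle 1, where the two references coincide. Later doses are chosen by the investigator, so neither reference isolates a dose effect. This is a reason to keep the study-baseline columns, not to leave out a paired comparison.
- **The alternative reference is imperfect.** The qualification reading can be 28 days old at treatment, or older if treatment is delayed, because qualification is not repeated. If PVR was still falling, change from it may understate the new injection's effect. This stands, and makes the added analysis supplementary.

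**Conclusion.** The gap is real and limited. In cycles 2 onward the descriptive PVR tables do not separate volume present before the injection from volume that appeared after it. In one patient up to 159 to 199 mL above study baseline can be attributed to the new cycle and dose, in the mean change and in the >100 to <200 mL band. The effect on a group mean is unknown; the 3.0 to 39.8 mL span rests on assumed shares of 5% to 20% and assumed excesses of 60 to 199 mL.

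The documents do not support the stronger inference that residual urine will be misattributed, or that the repeat-treatment safety results as a whole are unreliable. They give no share of patients retreated with a raised PVR, and cycle 1 is unaffected. Nor does the point bear on whether the retreatment limit is appropriate. What remains is an inexpensive improvement that would also show if carry-over is negligible.

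**What to change.** In SAP 6.6.3 keep all planned outputs, including the study-baseline columns. For each cycle from 2 on, by dose group, add:

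1. mean PVR change with 95% CI from the last PVR before that cycle's injection, which under the schedule is the qualification-visit value;
2. a shift table of PVR band at qualification against the highest band after the injection in that cycle.

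Label both as supplementary, and state that the reference reading can be up to 28 days old, or older after a delay, so the change may understate the injection's effect if PVR was still falling.

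The cost is one derived reference value and two added displays. Table 1 already requires PVR at the qualification visit, so no new data are needed and no clinical rule changes.

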2.1 Study Objectives

To evaluate the safety and efficacy of BOTOX for the treatment of urinary incontinence due to OAB in patients 12 to 17 years of age who have not been adequately managed with anticholinergic therapy. To evaluate the safety and efficacy of repeated BOTOX treatments in this patient population.

2.2 Clinical Hypotheses

BOTOX (1 or more of the treatment groups) has an acceptable safety profile when injected into the detrusor of patients 12 to 17 years of age with OAB. BOTOX (1 or more of the treatment groups) improves the symptoms of OAB as measured by a reduction from baseline in daytime urinary incontinence episodes.

3. Study Design

This is a multicenter, randomized, double-blind, parallel-group, multiple-dose study to evaluate the efficacy and safety of BOTOX in patients with urinary incontinence due to OAB who are 12 to 17 years of age. Patients will be evaluated during a screening period for eligibility. Eligible patients will be randomized and receive treatment on day 1 once all “day of treatment criteria” are fulfilled (see Section 5.9.1). Patients will initially be randomized via a central interactive voice response system (IVRS)/interactive web response system

(IWRS) and assigned a randomization number prior to treatment in a 1:1:1 ratio to receive a single treatment of 25 U, 50 U, or 100 U BOTOX (not to exceed 6 U/kg). Randomization will be stratified by baseline daytime urinary urgency incontinence episodes (a total of ≤ 6 episodes or > 6 episodes over the 2-day bladder diary collection period). During the screening period and on the days of bladder diary completion prior to scheduled clinic visits during the study, patients agree to a minimum fluid intake of 1500 mL/m² body surface area (BSA) and a maximum of 3000 mL/m² BSA per day. The study medication will be administered via cystoscopy as 20 intradetrusor injections of 0.5 mL each, sparing the trigone.

Patients will have posttreatment follow-up clinic visits at weeks 2, 6, and 12. Thereafter, patients who do not request retreatment will have alternating telephone and clinic follow-up visits every 6 weeks until they exit the study. In this study, patients can receive multiple treatments dependent upon the number and timing of patient requests/qualification for retreatment. Before receiving each retreatment patients will have to meet the qualification and “day of treatment criteria”. The dose received at any given retreatment will be determined by the investigator based on the response to the preceding blinded treatment. The investigator can elect to keep the dose the same or increase the dose compared with the preceding treatment (if it is deemed a decrease in dose is warranted, the patient will be exited from the study). The actual dose received remains blinded (unless the patient is requested to exit the study via the IVRS/IWRS, as described at the end of Section 5.5, or until the primary analysis has been reported as described in Section 7.7).

Request for retreatment can occur at any scheduled clinic or telephone visit or between scheduled visits from week 12 onwards. If a request occurs at a scheduled clinic visit, then that clinic visit will also become the qualification for retreatment visit, otherwise a qualification for retreatment clinic visit should occur within approximately 1 to 2 weeks of request. Patients exit the study once 96 weeks have elapsed since entry on day 1 and at least 12 weeks follow-up since their last study treatment has occurred (exit will therefore be between 96 and 108 weeks since study entry on day 1; the latter being for patients who received retreatment at week 96).

The primary efficacy measure is daytime urinary incontinence episodes, and the primary timepoint is week 12 after treatment 1.

4. Study Population and Entry Criteria

4.1 Number of Subjects

Approximately 108 patients will be randomized at approximately 35 to 45 sites in order to have an estimated 96 patients (32 per treatment group) based on an anticipated dropout rate of 10% by the primary timepoint of week 12 after treatment 1.

4.2 Study Population Characteristics

This study will include patients 12 to 17 years of age with urinary urgency incontinence due to OAB who have not been adequately managed with anticholinergics.

4.3 Inclusion Criteria

The following are requirements for entry into the study:

1. written informed consent has been obtained from the legally authorized representative and written minor assent has been obtained, in accordance with local laws and institutional review board (IRB)/independent ethics committee (IEC) requirements
2. written documentation has been obtained in accordance with the relevant country and local privacy requirements, where applicable (eg, Written Authorization for Use and Release of Health and Research Study Information (US sites) and written Data Protection consent (European sites))
3. male or female, aged ≥ 12 years to ≤ 17 years of age at the time of informed consent
4. patient has symptoms of OAB (frequency and urgency) with urinary incontinence for a period of at least 6 months immediately prior to screening, determined by patient history
5. patient experiences a total of ≥ 2 episodes of daytime urinary urgency incontinence in the 2-day patient bladder diary completed during the screening period (daytime is defined as time between waking up to start the day and going to bed to sleep for the night)
6. patient experiences urinary frequency, defined as an average of ≥ 8 micturitions (toilet voids) per day ie, a total of ≥ 16 micturitions in the 2-day patient bladder diary completed during the screening period

7. patient has not been adequately managed with 1 or more anticholinergic agents for the treatment of OAB in the opinion of the investigator. This includes patients who are still incontinent despite anticholinergic therapy, experiencing intolerable side effects, or are unwilling to continue to take the medication for any reason.
8. patient is willing and able to use CIC to empty the bladder at any time after study treatment if it is determined to be necessary by the investigator
9. patient agrees to a minimum fluid intake of 1500 mL/m² BSA, not to exceed 3000 mL/m² BSA per day, during the patient bladder diary completion days at screening and prior to clinic visits during the study (see Section 6.3.6 for further details)
10. negative urine pregnancy test for females who are postmenarche
11. patient is able to complete study requirements including completion of bladder diaries and HRQOL questionnaires (these can also be completed by the parent/legally authorized representative), and is likely to attend study visits in the opinion of the investigator

4.4 Exclusion Criteria

The following are criteria for exclusion from participating in the study:

1. patient has an uncontrolled systemic disease, or has previous or current diagnosis of malignancy
2. patient has symptoms of OAB due to any known neurological reason (eg, spina bifida, spinal cord injury, or cerebral palsy)
3. patient has a history of 2 or more UTIs treated with antibiotics within 6 months of randomization/day 1 or is taking prophylactic antibiotics to prevent chronic UTI
4. patient has a history or evidence of any pelvic or urological abnormalities, except OAB, including:
 - bladder neck surgery resulting in an open bladder neck, or reconstructive surgery of the lower urinary tract (eg, urostomy, urinary diversion, or bladder augmentation)
 - anatomical evidence of bladder outlet obstruction (including functional outlet obstruction), urethral or urethral valve obstruction/stricture at screening

- surgery of the urinary tract (including minimally invasive surgery) within 6 months of screening (except those listed above which are exclusionary for any time period)
 - circumcision within 1 month of screening
 - clinically relevant kidney abnormality, or clinically relevant vesicoureteric reflux, or disease of the bladder (other than OAB) that may affect bladder function
5. patient has predominance of stress incontinence, or “giggle” incontinence, or any condition other than OAB that in the investigator’s opinion may account for the patient being incontinent
 6. patient has unmanaged, unresolved bowel problems (eg, constipation, encopresis)
 7. patient currently uses or plans to use medications or therapies to treat symptoms of OAB, including nocturnal enuresis or nocturia. Patients previously receiving these medications must have discontinued their use prior to the start of the first screening procedure as follows:
 - for desmopressin, at least one day prior
 - for anticholinergic therapy, at least 7 days prior
 - for intravesical anticholinergic therapy, at least 4 weeks prior
 - for mirabegron, at least 14 days prior
 8. patient currently uses or plans to use an implantable or nonimplantable electrostimulation/neuromodulation device for treatment of OAB. (If a nonimplantable device is used, it must be discontinued at least 7 days prior to the first screening procedure; if a device is implanted, it must be inactive for at least 4 weeks prior to the first screening procedure; neither should be used during the study.)
 9. patient plans to start using psychiatric medications or medications for attention deficit hyperactivity disorder during the study. If the patient is already using such medications they should be on a stable dose prior to randomization/day 1 and agree to remain on the same dose during the study if possible when medically indicated.
 10. patient uses CIC or an indwelling catheter to manage their OAB
 11. patient has had previous or current botulinum toxin therapy of any serotype for any urological condition, or treatment with botulinum toxin of any serotype within 3 months of randomization/day 1 for any other condition or use

12. patient has been treated with intravesical capsaicin or resiniferatoxin within 12 months of screening
13. patient has a PVR urine volume of > 40 mL at screening. The PVR measurement can be repeated once on the same day; the patient is to be excluded if the repeated measure is above 40 mL.
14. patient has a daytime (waking hours) total volume of urine voided > 3000 mL, collected over one daytime period during the 2-day bladder diary collection period prior to randomization/day 1
15. postmenarche female patients of childbearing potential who are pregnant, nursing, or planning to become pregnant during the study (postmenarche female patients must also either be sexually abstinent or use another acceptable form of contraception – see Section 4.5.1.1)
16. patient has known allergy or sensitivity to components of any botulinum toxin preparation (including the study medication preparation), anesthetics or antibiotics to be used during the study
17. patient has hemophilia, or other clotting factor deficiencies, or disorders that cause bleeding diathesis
18. patient cannot withhold any antiplatelet, anticoagulant therapy, or other medications with anticoagulant effects for 3 days prior to randomization/day 1. Note: some medications may need to be withheld for > 3 days, per clinical judgment of the investigator (see Section 4.5.2, Prohibited Medications/Treatments for additional details)
19. patient has any medical condition that may put them at increased risk with exposure to BOTOX including diagnosed myasthenia gravis, Eaton-Lambert syndrome, or amyotrophic lateral sclerosis
20. current enrollment in an investigational drug or device study, or participation in such a study within 30 days of entry into this study (or longer if local requirements specify)
21. patient has a condition or is in a situation which in the investigator's opinion may put the patient at significant risk, may confound the study results, or may interfere significantly with the patient's participation in the study

